2.8.1.1 Adverse events of special interest / grouping of AEs

Safety topics of interest, such as risks defined in the Safety Profiling Plan (SPP), Risk Management Plan or topics of interest regarding signal detection or routine analysis are defined in the Program Case Retrieval Sheet.

The crude incidence and exposure-adjusted incidence rates (only for level 1) will be summarized. In addition, listings will be provided presenting which patients experienced which risk.

The version of the Case Retrieval Sheet used for the analyses will be described in a footnote. This includes MedDRA version and Customized MedDRA Query (CMQ) and Novartis MedDRA Query (NMQ) dictionary date.

2.8.2 Deaths

A listing for deaths will be presented. The listing will include trial period when death occurred, and whether the death is on treatment, post-treatment follow-up, or screening will be identified.

2.8.3 Laboratory data

The general guideline for laboratory summaries(including Vital sign and ECGs) are as below:

- All the summary of lab outputs (newly occurring notables, maximum changes, shift tables, by visit summary statistics) will consider the "on-treatment" data, i.e., all assessments within last dose plus 84 days.

Follow up visit summary: using CRF visits (including early discontinued patients), i.e., not applying visit window and cut-off day 84. Summary of follow up visit outputs will be provided. The listing will provide follow up visit records.

- All records are displayed in the listing with the on-treatment flag, i.e., occurred within last dose plus 84 days- yes or no.

The summary of laboratory evaluations will be presented for three groups of laboratory tests (hematology, clinical chemistry, and urinalysis). In addition to the individual laboratory parameters the ratios "total cholesterol / HDL" and "apolipoprotein B / apolipoprotein A1" will be derived and summarized.

For urinalysis, frequency tables will be presented.

Descriptive summary statistics for the change from baseline to each study visit will be presented. These descriptive summaries will be presented by laboratory test and treatment group. Change

from baseline will only be summarized for patients with both baseline and post baseline values and will be calculated as:

$$\text{change from baseline} = \text{post baseline value} - \text{baseline value}$$

For each parameter, the maximum change (maximum decrease and maximum increase) from baseline, if appropriate for each study phase, will be analyzed analogously.

In addition, shift tables will be provided for all parameters to compare a patient's baseline laboratory evaluation relative to the visit's observed value. For the shift tables, the normal laboratory ranges will be used to evaluate whether a particular laboratory test value was normal, low, or high for each visit value relative to whether or not the baseline value was normal, low, or high. If appropriate, the shifts to the most extreme laboratory test value within entire treatment period will be presented as well (including category "high and low"). These summaries will be presented by laboratory test and treatment group.

The following laboratory parameters will be analyzed with respect to numerical Common Terminology Criteria for Adverse Events (CTCAE) grades, given in [Table 2-3](#): hemoglobin, platelets, white blood cell count, neutrophils, lymphocytes, creatinine, total bilirubin (TBL), gamma-glutamyl transferase (GGT), alanine aminotransferase (ALT), aspartate aminotransferase (AST), alkaline phosphatase (ALP), glucose, cholesterol, triglycerides (TG).

These summaries will be split into hematology and chemistry.

Table 2-4 CTCAE grades for laboratory parameters to be analyzed

CTCAE v4.0 Term	Grade 1	Grade 2	Grade 3	Grade 4
HGB decreased (Anemia)	<LLN – 100 g/L	<100 – 80 g/L	<80 g/L	
Platelet count decreased	<LLN – 75.0 x10e9 /L	<75.0 - 50.0 x10e9 /L	<50.0 – 25.0 x10e9 /L	<25.0 x 10e9 /L
White blood cell decreased	<LLN - 3.0 x 10e9 /L	<3.0 - 2.0 x 10e9 /L	<2.0 - 1.0 x 10e9 /L	<1.0 x 10e9 /L
Neutrophil count decreased	<LLN - 1.5 x 10e9 /L	<1.5 - 1.0 x 10e9 /L	<1.0 - 0.5 x 10e9 /L	<0.5 x 10e9 /L
Lymphocyte count decreased	<LLN - 0.8 x 10e9/L	<0.8 - 0.5 x 10e9 /L >1.5 - 3.0 x	<0.5 - 0.2 x 10e9 /L	<0.2 x 10e9 /L
Creatinine increased*	>1 - 1.5 x baseline; >ULN - 1.5 x ULN	>1.5 - 3.0 x baseline; ULN	>3.0 baseline; >3.0 - 6.0 x ULN	>6.0 x ULN
TBL increased	>ULN - 1.5 x ULN	>1.5 - 3.0 x ULN	>3.0 - 10.0 x ULN	>10.0 x ULN
GGT increased	>ULN - 2.5 x ULN	>2.5 - 5.0 x ULN	>5.0 - 20.0 x ULN	>20.0 x ULN
ALT increased	>ULN - 3.0 x ULN	>3.0 - 5.0 x ULN	>5.0 - 20.0 x ULN	>20.0 x ULN
AST increased	>ULN - 3.0 x ULN	>3.0 - 5.0 x ULN	>5.0 - 20.0 x ULN	>20.0 x ULN
ALP increased	>ULN - 2.5 x ULN	>2.5 - 5.0 x ULN	>5.0 - 20.0 x ULN	>20.0 x ULN
Glucose increased (Hyperglycemia)	>ULN - 8.9 mmol/L	>8.9 - 13.9 mmol/L	>13.9 - 27.8 mmol/L	>27.8 mmol/L
Glucose decreased (Hypoglycemia)	<LLN - 3.0 mmol/L	<3.0 - 2.2 mmol/L	<2.2 - 1.7 mmol/L	<1.7 mmol/L
Cholesterol high	>ULN - 7.75 mmol/L	>7.75 - 10.34 mmol/L	>10.34 - 12.92 mmol/L	>12.92 mmol/L
Hypertriglyceridemia	1.71 - 3.42 mmol/L	>3.42 - 5.7mmol/L	>5.7 - 11.4 mmol/L	>11.4 mmol/L

*Note: for "creatinine increased" the baseline criteria do not apply

Shift tables will be presented comparing baseline laboratory result (CTCAE grade) with the worst results (expressed in CTCAE grade) during entire treatment period analyzed. Of note, baseline will be defined as last assessment prior to first dosing in initial treatment phase. Patients with abnormal laboratory values will be listed and values outside the normal ranges will be flagged.

Summaries for newly occurring or worsening clinically notable lipid abnormalities will also be provided cumulatively for each of the following parameters and categories:

- HDL:
 - \leq LLN
 - $<0.8 \times$ LLN
- LDL, cholesterol, triglycerides:
 - \geq ULN
 - $>1.5 \times$ ULN
 - $>2.5 \times$ ULN

Newly occurring or worsening liver enzyme abnormalities will also be summarized based on the event criteria given in [Table 2-4](#):

Table 2-5 Liver-related events

Parameter	Criterion
ALT	>3xULN; >5xULN; >8xULN; >10xULN, >20xULN
AST	>3xULN; >5xULN; >8xULN >10xULN; >20xULN
ALT or AST	>3xULN; >5xULN; >8xULN >10xULN; >20xULN
TBL	>1.5xULN, >2xULN, >3xULN,
ALP	>2xULN, >3xULN, >5xULN
ALT or AST & TBL	ALT or AST >3xULN & TBL >2xULN; ALT or AST >5xULN & TBL >2xULN; ALT or AST >8xULN & TBL >2xULN; ALT or AST >10xULN & TBL >2xULN
ALP & TBL	ALP >3xULN & TBL >2xULN ALP >5xULN & TBL >2xULN
ALT or AST & TBL & ALP	ALT or AST >3xULN & TBL >2xULN & ALP <2xULN (Hy's Law laboratory criteria) Note: elevated ALP may suggest obstruction as a consequence of gall bladder or bile duct disease; ALP may also be increased in malignancy. FDA therefore terms Hy's Law cases as indicators of pure hepatocellular injury . This does not mean that cases of ALT or AST >3xULN & TBL >2xULN & ALP ≥2xULN may not result in severe DILI.

Notes:

- 1) In studies which enroll patients with pre-existing liver disease, baseline LFT may be increased above ULN; in such a case it is meaningful to add the condition "and worse than baseline" to the abnormality criteria
- 2) In case an Adjudication Committee is in place it may be meaningful to summarize all abnormalities classed as e.g., *definitely/probably* (depending on the categories used) related to study treatment

For a combined criterion to be fulfilled, all conditions have to be fulfilled on the same visit. The criteria are not mutually exclusive, e.g. a patient with ALT = 6.42xULN is counted for ALT >3xULN and ALT >5x ULN.

Individual patient data listings will be provided for patients with newly occurring or worsening abnormal laboratory data. Data of patients with newly occurring or worsening liver enzyme abnormalities will be listed in an additional listing.

Box plots will be presented for selected laboratory parameters: WBC, neutrophils, and liver (ALP, AST, ALT, bilirubin) and lipid (cholesterol, HDL, LDL, triglycerides) parameters.

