 A PPD skin test can be performed at any time during the screening period, but it must be read within 72 hours and before baseline.

 A chest x-ray or MRI is required if it was not performed and evaluated within 3 months prior to screening. The x-ray should be performed after it is certain the patient meets inclusion/exclusion criteria in order to minimize unnecessary exposure to radiation. The x-ray may be replaced by a MRI assessment.

 AEs/SAEs occurring after the patient has signed the informed consent must be captured on the appropriate eCRF page.

 Sample must be obtained in the fasting state.

\* For all patients who discontinue the study, the investigator should ensure that the patient completes an end of treatment visit (corresponds to the last visit for the patient's current treatment period) 4 weeks after last study treatment to complete assessments shown for Week 24 (Treatment period 1) or Week 52 (Treatment period 2) in [Table 6-1](#), and also returns after an additional 8 weeks for a final follow-up visit, F60 in [Table 6-1](#) (12 weeks after last study treatment). The final visit should be performed before any new treatment is initiated.

\*\*Assessment for weight, Lipid and ECG at week 24 should be done only for patients who discontinue during treatment period 1.

\*\*\* Hepatitis B and/or hepatitis C and/or HIV serology testing should be performed during screening epoch prior to initiation of therapy. These assessments will be documented in source records only and will not be entered into the eCRF.

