#### **6.5.6.2 Clinical chemistry**

Serum chemistries will include glucose, urea, creatinine, total bilirubin, AST (SGOT), ALT (SGPT), GGT, alkaline phosphatase, sodium, potassium, bicarbonate, calcium, phosphorous, total protein, albumin, and uric acid.

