#### **6.5.6.3 Lipid panel**

A lipid profile, including high density lipoprotein (HDL), low density lipoprotein (LDL), cholesterol and, triglycerides will be measured from a fasting blood sample.

A cardiovascular profile including lipoprotein(a), apolipoprotein B, apolipoprotein A-1, and adiponectin will be measured from a fasting blood sample.

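### Glucose outputs compare a baseline that is probably fasting with later samples of mixed fasting status, which may bias the maximum increase and the hyperglycaemia shift upward

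*SAP*

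**What the plan says.** **Which samples are fasting.** Protocol 6.5.6.2 puts glucose in clinical chemistry ("Serum chemistries will include glucose, urea, creatinine, total bilirubin", and so on) and states no fasting condition. Protocol 6.5.6.3 does state one for two other panels: "A lipid profile, including high density lipoprotein (HDL), low density lipoprotein (LDL), cholesterol and, triglycerides will be measured from a fasting blood sample" and "A cardiovascular profile including lipoprotein(a), apolipoprotein B, apolipoprotein A-1, and adiponectin will be measured from a fasting blood sample". Footnote 8 of Protocol Table 6-1 reads "Sample must be obtained in the fasting state". The row that carries this mark is not in the text available to us, and the chemistry row as it appears there has no footnote mark. Protocol 6.5.6 leaves collection details to a laboratory manual, which was not supplied.

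**What is done with glucose.** SAP 2.8.3 plans "Descriptive summary statistics for the change from baseline to each study visit will be presented", the maximum increase and decrease for each parameter, shift tables on normal ranges, and the CTCAE shift: "Shift tables will be presented comparing baseline laboratory result (CTCAE grade) with the worst results (expressed in CTCAE grade) during entire treatment period analyzed". In SAP Table 2-4, hyperglycaemia Grade 1 begins just above the ULN, with no fasting qualifier. Baseline is the last value before the first dose (SAP 2.1.1). Nothing in the SAP separates glucose by fasting status.

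**Comparator.** There is none (Protocol 3.4).

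**The concern.** Glucose depends on recent meals. If the baseline sample is fasting and some later samples are not, part of any observed rise reflects the sampling schedule. Outputs that take the largest or worst value over the whole period are the most exposed, because one fed sample is enough to move a patient up a grade.

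In a randomised trial the same artefact would appear in both arms and cancel in the comparison. Here it cannot be separated from an effect of secukinumab. None of the first four post-baseline visits (Weeks 1-4) has a fasting panel, and that is where an early drug effect would be looked for. The safety objective names clinical laboratory values, and the study is meant to support registration.

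**Working it through.** The documents give no figure for glucose or fasting, so there is no stated result to reproduce. The check has two parts.

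**1. How often chemistry coincides with a fasting panel**

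Input: the windows in SAP Table 2-1. That table is flattened in extraction, so the visits were confirmed from window limits, which should be midpoints between scheduled days (day = 7 × week + 1).

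| Column | Visits | Midpoint | Printed limit |
|---|---|---|---|
| Lipids | 8 and 16 | (57 + 113)/2 = 85 | 85 |
| Lipids | 16 and 52 | (113 + 365)/2 = 239 | 239 |
| Cardiovascular | 16 and 24 | (113 + 169)/2 = 141 | 141 |
| Cardiovascular | 24 and 52 | (169 + 365)/2 = 267 | 267 |
| Laboratory | 28 and 40 | (197 + 281)/2 = 239 | 239 |
| Laboratory | 40 and 52 | (281 + 365)/2 = 323 | 323 |

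- Laboratory windows after baseline, to Week 52: Weeks 1, 2, 3, 4, 8, 12, 16, 20, 24, 28, 40, 52 (12).
- Fasting panels: baseline; lipids at Weeks 8, 16, 52; cardiovascular at Weeks 16, 24, 52. Union after baseline: Weeks 8, 16, 24, 52.
- Overlap: 4 of 12. No stated fasting rule: 12 − 4 = 8 (Weeks 1, 2, 3, 4, 12, 20, 28, 40). With Week 60 it is 9 of 13.

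Week 24 rests on the cardiovascular panel alone, because Protocol Table 6-1 limits Week 24 lipids to patients who discontinue in period 1. The chemistry row of that table, as extracted, marks every visit from the second screening visit on. That would be 16 post-baseline visits to Week 52, of which 4 have a fasting panel. On either count, most later chemistry draws have no fasting rule.

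**2. Illustration of size, with no drug effect**

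Every glucose value here is an assumption: fasting mean 5.1 mmol/L, between-patient SD 0.4, within-patient SD 0.3.

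*By-visit mean.* Spurious change = fed share × mean meal increment. With half the samples fed and increments of 0.5 to 1.5 mmol/L, this is 0.5 × 0.5 = 0.25 to 0.5 × 1.5 = 0.75 mmol/L. At a fasting-panel visit it is 0.

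*Worst value with no fasting difference.* Let b be the patient's true level and Φ = Φ((ULN − b)/0.3). Among patients normal at baseline, the chance that the worst of k later values exceeds the ULN is E[Φ(1 − Φ^k)] / E[Φ], averaged over b.

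| ULN (mmol/L) | k = 4 | k = 12 |
|---|---|---|
| 6.1 | 5% | 10% |
| 5.6 | 25% | 40% |

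These percentages come only from comparing one baseline value with the worst of several.

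*Worst value with some fed samples.* Simulation with 4 fasting samples and 8 samples without a rule:

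| ULN | Fed share of the 8 | Mean increment | Worst value above ULN |
|---|---|---|---|
| 6.1 | 10% | 0.5 | 17% (fixed increment) to 21% (exponential) |
| 6.1 | 50% | 0.5 | 32% (fixed) to 51% (exponential) |
| 6.1 | 50% | 1.5 | 90% (exponential) to 95% (fixed) |
| 7.0 | 50% | 0.5 | under 1% (fixed) to 13% (exponential) |
| 5.6 | 50% | 1.5 | 96% (exponential) to 99% (fixed) |

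The direction is upward whenever there is a meal increment. The size is set by the fed share, the increment and the ULN, none of which the documents give.

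**The case against.** A reader might infer more: that glucose is fasting at baseline, that later samples are fed, and that the tables will therefore show a false rise of a definite size. The documents do not support this.

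- A fasting baseline is inferred from the visit shared with the lipid and cardiovascular panels. It is likely, but no section says it.
- The absence of a fasting rule does not mean the patient has eaten. The laboratory manual may ask for fasting at every draw, or record fasting status.
- The illustration runs from under 1% to about 99% on outside assumptions, so no single figure can be put on the bias.
- A Grade 1 cell in a shift table is not an adverse event. Protocol 7.1 requires symptoms, clinical significance or a need for therapy.
- On the same premise, Weeks 8, 16, 24 and 52 compare fasting with fasting. The by-visit tables might reveal a rise that follows the schedule.
- Glucose is not among the identified risks in Protocol 3.6 or the notable criteria in Protocol Table 13-1.

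All of this stands, and it limits the point to a possible bias in particular outputs. It does not remove the point: the maximum increase and the worst-grade shift combine all visits, so the by-visit tables do not correct them, and the SAP gives no rule for reading them.

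A further objection is that restricting glucose to four post-baseline visits would discard Weeks 1-4 and could hide a real early rise. That is correct, and it is why the all-sample table must stay.

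**Conclusion.** The point holds as a possible upward bias. Exposed outputs are the by-visit glucose change at Weeks 1-4, 12, 20, 28 and 40, the maximum increase, and the shift from baseline to worst hyperglycaemia grade. By-visit comparisons at Weeks 8, 16, 24 and 52 are not exposed.

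The structural count is 8 of 12 post-baseline chemistry windows without a stated fasting rule. It rests on the flattened SAP Table 2-1, supported by the window midpoints. The size of the bias cannot be derived from the documents. Of any excess over the ULN, about 10 percentage points (assumed ULN 6.1 mmol/L) would arise from taking the worst of 12 values, with no fasting difference at all.

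The conclusion assumes that baseline chemistry is drawn with the fasting panels and that the laboratory manual does not require fasting for chemistry. If the manual does, one sentence in the SAP settles the matter.

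**What to change.** In SAP 2.8.3:

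1. Present the glucose maximum increase and the hyperglycaemia CTCAE shift for samples from the fasting-panel visits (baseline and Weeks 8, 16, 24 and 52), or by actual fasting status if it is recorded.
2. Keep the all-sample version beside it, labelled as mixed fasting status, so that a rise at Weeks 1-4 remains visible.
3. In the by-visit glucose table, mark the visits at which fasting was not required.
4. Leave hypoglycaemia grading on all samples.

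The cost is SAP wording and one extra table, with no new samples. The fasting-visit table has 4 post-baseline values per patient instead of 12, and classification by visit assumes that patients followed the fasting instruction. The Week 24 analysis is already done (SAP 2.14), so the change would apply to the Week 52 and final outputs, and the difference in presentation should be noted.

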2.8.4 Other safety data

2.8.4.1 ECG

Summaries of ECG are presented for all "on-treatment" data (see section 2.8.3).

The following quantitative variables may be summarized: ventricular rate, RR interval, PR interval, QRS duration, QT interval, and corrected QT interval (QTc). Both Bazett (QTcB) and Fridericia (QTcF) corrections will be presented for QTc.

QTc will be summarized by computing the number and percentage of patients with:

- QTc > 500 msec
- QTc > 480 msec
- QTc > 450 msec
- QTc changes from baseline > 30 msec
- QTc changes from baseline > 60 msec
- PR > 250 msec

Summary statistics will be presented for ECG variables by visit.

In addition, shift tables comparing baseline ECG interpretation (normal, abnormal, not available, total) with the worst on study interpretation (normal, abnormal, not available, total) will be provided.

A listing of all newly occurring or worsening abnormalities will be provided, as well as a by-patient listing of all quantitative ECG parameters.

2.8.4.2 Vital signs

Summaries of vital signs are presented for all “on-treatment” data (see section 2.8.3).

Analysis in vital sign measurement using descriptive summary statistics for the change from baseline for each post-baseline visit will be performed. These descriptive summaries will be presented by vital sign. Change from baseline will only be summarized for patients with both baseline and post-baseline values and will be calculated as:

$$\text{change from baseline} = \text{post-baseline value} - \text{baseline value}$$

The number and percentage of patients with newly occurring notable vital signs will be presented. Criteria for notable vital sign abnormalities are provided in Table below.

Table 2-6 Criteria for notable vital sign abnormalities

Vital sign (unit)	Notable abnormalities
Systolic blood pressure (mmHg)	≥ 140 mmHg or < 90 mmHg
Diastolic blood pressure (mmHg)	≥ 90 mmHg or < 60 mmHg
Pulse (bpm)	> 100 bpm or < 60 bpm

Data of patients with newly occurring notable vital signs abnormalities will be listed in an additional listing.

2.8.4.3 Immunogenicity

A patient listing of immunogenicity (anti-AIN457 antibodies) will be presented.

2.9 Pharmacokinetic endpoints

All patients with concentration data will be included in the pharmacokinetic data analysis.

Pharmacokinetic variables

Serum concentrations will be expressed in mass per volume units. All concentrations below the limit of quantification as well as missing data will be labeled as such in the concentration data listings. PK concentrations will be summarized by visit. In addition to mean, standard deviation (SD), coefficient of variation (CV), median and quartiles, the geometric mean and geometric coefficient of variation (CV) and n(log) will be presented. The formula for deriving the geometric mean and CV (%) is as following:

- $CV (\%) = (SD/\text{mean}) * 100$,
- geometric mean = $\exp((\text{sum of log transformed data}) / (\text{number of non-missing data points after log transformation}))$,
- geometric CV = $\sqrt{\exp(\text{variance of log-transformed data}) - 1} * 100$.

In addition, sample number, concentration, sample date, sample time at pre-dose and minutes pre-dose will be listed. All data will be listed.

Statistical methods for pharmacokinetic analyses

Pharmacokinetic data of the study treatment will be analyzed with a population pharmacokinetic mixed effects model. The analysis will be based on a pooled data set, including pharmacokinetic samples from previous studies. The modeling approach will be further detailed in a modeling plan. Results will be reported separately.

2.10 PD and PK/PD analyses

An indirect response model, driven by study treatment concentration, will be used to characterize the time course of efficacy response. Further details of the modeling approach will be specified in a modeling plan. Results will be reported separately.

2.11 Patient-reported outcomes

The following patient-reported outcomes will be summarized. In general, the derived scores will be calculated when all variables for calculating the scores are non-missing otherwise specified.

For binary efficacy variables, analyses with the non-respondent imputation described in 2.5.3 and with observed case will be performed.

SF-36

The Short Form Health Survey (SF-36) is a widely used and extensively studied instrument to measure health-related quality of life among healthy subjects and patients with acute and chronic conditions. It consists of eight subscales that can be scored individually: Physical Functioning, Role-Physical, Bodily Pain, General Health, Vitality, Social Functioning, Role-Emotional, and Mental Health. Two overall summary scores, the Physical Component Summary (PCS) and the Mental Component Summary (MCS) also can be computed. The SF-

36 has proven useful in monitoring general and specific populations, comparing the relative burden of different disease, differentiating the health benefits produced by different treatments, and in screening individual patients. SF-36 scoring will be done by an independent vendor.

[figure not shown]
The following variables will be evaluated:

[figure not shown]
- SF-36 domain scores (based on a scale of 0-100).
- SF-36 PCS and MCS scores (norm-based scores).
- SF-36 PCS and MCS responder (improvement of ≥ 2.5 points, [Lubeck 2004](#))

[figure not shown]
ASQoL

The ASQoL is a self-administered questionnaire designed to assess health-related quality of life in adult patients with Ankylosing Spondylitis. The ASQoL contains 18 items with a dichotomous yes/no response option. A single point is assigned for each "yes" response and no points for each "no" response resulting in overall scores that range from 0 (least severity) to 18 (highest severity). As such, lower score indicate better quality of life. Items include an assessment of mobility/energy, self-care and mood/emotion. The recall period is "at the moment," and the measure requires approximately 6 minutes to complete.

At least 15 answered questions are required to be able to calculate ASQoL using mean imputation, $18*(\text{sum of answered})/(\text{number answered})$ ([Doward, 2003](#))

[figure not shown]

[figure not shown]

[figure not shown]

[figure not shown]
